11.5.8.6 Procedures for Reporting Adverse Events and Serious Adverse Events

In the case of an AE (Serious and Significant Non-Serious) or Medical Treatment (non-AE), the Investigator must:

- Report the AE or Medical Treatment to the Medical Monitor within 24 hours of knowledge of the event using the Sponsor-provided form (SAE/UDE reporting form) by emailing the completed form to the Medical Monitor

- Indicate on the Initial SAE/UADE reporting form whether the SAE/UADE is presumed to be not study-related, lens-related, solution-related, or both lens/solution related.
- Ensure that the subject's identity is protected and the subject's identifiers in the clinical trial are properly mentioned on the form.
- BEGIN TREATMENT OF THE AE IMMEDIATELY BY A SUITABLY LICENSED EYE CARE PROFESSIONAL.
- Enter the SAE/UADE into the eCRF within 3 business days of submitting the Initial AE/Medical Treatment Notification Form.
- Continue to update the eCRF, if applicable, each time the subject is seen during the management of the incident and at resolution of the incident. Whenever possible, it is suggested that the Investigator take photographs of all AEs and forward them to the Sponsor.
- Cases requiring medical treatment will be evaluated by the Sponsor. Upon review of the medical treatment, Bausch + Lomb Clinical Operations representatives may contact the Investigator to request further information concerning the treatment.
- Submit all bills, prescription receipts, and culture reports/fees related to the AE to Bausch + Lomb Clinical Operations. Expenses incurred for study-related medical treatment will be paid by Bausch + Lomb Clinical Operations.

Guidelines for Reporting Pregnancies

All female subjects of childbearing potential must use an effective method of birth control during the study, to include 2 weeks after last visit, in a manner such that risk of contraceptive failure is minimized. Abstinence is allowed as a birth control method. Before enrolling a female subject of childbearing potential, the Investigator must review the following information about study participation:

- Informed consent requirement
- Contraceptives in use

Following review of this information and appropriate counseling, the Investigator or designee and the subject must sign the informed consent before study enrollment. During the study, all female subjects of childbearing potential should be instructed to contact the Investigator immediately if they suspect they might be pregnant (eg, missed or late menstrual period).

If a subject or Investigator suspects that the subject may be pregnant prior to study enrollment, the study lens must be withheld until the results of laboratory pregnancy testing are available. If pregnancy is confirmed, the subject must not receive study lens and must not be enrolled in the study. If pregnancy is suspected while the subject is receiving study treatment, the study lens must immediately be withheld until the result of pregnancy testing is known. If pregnancy is confirmed, the study lens will be permanently discontinued and the subject will be followed until the pregnancy comes to term. A Pregnancy Report form will be submitted to the Sponsor, initially and at the end of the pregnancy, which includes the outcome of the pregnancy and any complications occurring during the pregnancy or the delivery.

All confirmed pregnancies must be immediately reported to the Medical Monitor within 24 hours of the Investigator's awareness of the pregnancy. All confirmed pregnancies must be reported via confirmed facsimile/email transmission and must be submitted on a Pregnancy Report form within 24 hours of the Investigator's awareness of the pregnancy using the same reporting as procedure for an SAE. Although pregnancy occurring in a clinical study is not considered to be an AE or SAE, any pregnancy complication or elective termination of a pregnancy, for medical reasons, will be recorded as an AE or SAE. Any serious complications or event resulting from the pregnancy should be reported to the Sponsor within 24 hours on a SAE/UADE form along with the Pregnancy Report form.

11.5.9 Obligations of the Sponsor

During the study, the Sponsor will report in an expedited manner:

- All unexpected SAEs possibly related to IMP (SUSAR), to the Health Authorities, as appropriate and to the Investigators.
- All SAEs possibly related to the Test Product, to the IRB/IEC as appropriate and to the Investigators.
- All UADEs related to the Test Product, to Health Authorities, to the IRB/IEC as appropriate and to Investigators.

Any AE not listed as an expected event in the package insert or in this protocol will be considered as unexpected.

The Sponsor will report all safety observations made during the conduct of the trial in the clinical study report.

11.5.10 Reporting Device Deficiencies

A device deficiency is defined as an inadequacy of a medical device with respect to its identity, quality, durability, reliability, safety or performance. Device deficiencies include malfunctions, use errors, and inadequate labeling. All device deficiencies will be reported to the Sponsor and its representatives on a Device Deficiency Report form.

Investigators must evaluate, record, and report via applicable forms any complaints/deficiencies, or malfunctions that could potentially lead to a SAE during this trial to the Sponsor and its representative without unjustified delay. As required, such reports may be provided to the reviewing IRB per their established reporting procedures and the FDA by the Investigator. Upon the Sponsor's request, Investigators must supply any additional information related to the safety reporting of a particular event.

The contact for reporting device deficiencies is:

[REDACTED]
[REDACTED]

The Sponsor shall review all device deficiencies and determine and document in writing whether they could have led to a SAE. In the event of a disagreement between the Sponsor and the Investigator(s), the Sponsor shall communicate both opinions to the reviewing IRB per their established reporting procedures and the health authority.

12 Statistics

12.1 Determination of Sample Size

12.1.1 Primary Effectiveness Endpoints

The null hypothesis is that the difference in the proportion of subjects with both eyes "0.04 or Better" between the test group (π_T) and the control group (π_C) is less than or equal to the negative value of the non-inferiority margin ($-\delta$). The alternative hypothesis is that the difference in proportions is greater than the negative value of the non-inferiority margin.

$$H_0: \pi_T - \pi_C \leq -\delta$$

$$H_1: \pi_T - \pi_C > -\delta$$

In a previous evaluation of Biotrue ONEday for Astigmatism Soft Contact Lenses, 92.5% of subjects with baseline logMAR BSCVA of 0.04 or better achieved the primary effectiveness endpoint of this study at the follow-up visit. Consequently 92.5% is the expected percentage of subjects "0.04 or Better" in the Test and Control groups. The non-inferiority margin will be set at 10% and the lower confidence limit will be compared to -10%.

A one-sided alpha risk of 0.025 (eg, a two-sided 95% confidence interval) will be used to test the hypothesis.

When the sample size in each group is 109 subjects, a two-group large-sample normal approximation test of proportions with a one-sided 0.025 significance level will have 80% power to reject the null hypothesis that the test is inferior to the control (the difference in proportions, $\pi_T - \pi_C$, is -0.10 or less) in favor of the alternative hypothesis that the test lens is non-inferior, assuming that the expected difference in proportions is 0.000 and the proportion in the standard group is 0.925.

12.1.2 Overall Power and Sample Size

In order to allow for dropouts of up to 10%, at least approximately $109/(1-0.1) \approx 122$ subjects will be enrolled in each treatment group for a total enrollment of approximately 244 subjects.

12.2 Analysis Populations

12.2.1 Intention-to-Treat (ITT) Population

The ITT Population will include all randomized subjects (and both of their eyes) who are deemed eligible based on pre-randomization eligibility assessments. Subjects in the ITT Population will be included in summaries under the lens type to which they were randomized.

12.2.2 Per Protocol Population

The PP Population will include all randomized subjects without major protocol deviations who complete the study through Visit 3 (Days 6 - 10). Major protocol deviations affecting only one eye will result in the exclusion of both eyes from eye level summaries.

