7.1 Description of the Protocol

This is a multicenter, randomized 1:1, parallel-group, bilateral, Investigator-masked study at 13 investigative sites in the United States (US) on a population including approximately 50% Chinese subjects (maternal and paternal grandparents born in China), comparing Biotrue ONEday for Astigmatism Soft Contact Lens (Test) to 1-Day Acuvue Moist for Astigmatism contact lens (Control).

Approximately 244 subjects will be randomized in this 3 month, parallel-group, bilateral, Investigator-masked study at 13 investigative sites in the US enrolling Chinese subjects. In order for submission of this study to the Chinese Regulatory Authorities, approximately 244 randomized subjects will be enrolled, including those of Chinese origin with 2nd generation Chinese ancestry with both sets of grandparents being of Chinese origin, with a documented family tree worksheet kept with the subject's source documents.

A person with Chinese ancestry would be defined as a subject with both sets of grandparents born in China. A person with 3 Chinese grandparents and one grandparent of full Chinese ancestry who was not born in China will be defined as “Non-Chinese”.

At the Screening Visit, approximately half of the subjects will be randomized to receive Biotrue ONEday for Astigmatism Soft Contact Lenses (Test) and the other half will be randomized to receive 1-Day Acuvue Moist for Astigmatism contact lenses (Control). Both groups will wear their assigned lenses on a daily wear basis throughout the study with visits planned for Screening (Visit 1), Dispense (Visit 2), 1 week (Visit 3), 1 Month (Visit 4), 3 Months (Visit 5), and/or a final Exit Visit.

Subjects will be randomized sequentially. Subjects will be dispensed product according to the treatment arm corresponding to their randomization and will be unmasked.

Subjects will be instructed to use their habitual rewetting drops as needed during the study. Subjects will be provided with study lenses as part of the dispensing package and instructions for the use and care for the test articles.

Subjects will also be required to complete a paper diary. Subjects will be provided with a reminder to complete the diary to capture wear experience on a weekly basis until they exit the study.

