7.2 Duration of Study Participation

7.2.1 Duration of Study Participation for Each Subject

Investigators will have up to 3 weeks between the Screening and Dispensing Visit.

Subjects will be followed for 3 months (unless discontinued or lost to follow-up) and must adhere to the following schedule:

Visit	Target	Acceptable Visit Range
V1: Screening Visit	None	Day -21 to Day -14
V2: Dispensing Visit	Day 1	NA
V3: 1-Week Follow-up Visit	Day 8	Day 6 – 10
V4: 1-Month Follow-up Visit	Day 31	Day 28 – 36
V5: 3-Month Follow-up Visit	Day 92	Day 92 – 102

NA = not applicable

Notes: The 3-month follow-up visit must occur no earlier than Day 92. There is no Day 0 in this numbering scheme. The day prior to dispensing is Day-1.

The visit range is based on the date test articles are initially dispensed (Dispensing Visit). A visit scheduling table will be provided in the initial study shipment to aid the Investigator in scheduling Follow-up Visits.

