9.4 Protocol Deviations

The date of and reason for deviations will be documented in all cases. Significant or major protocol deviations impacting the safety of the subject or the integrity of the study must be reported by the Investigator to the IRB immediately. Reporting of all other protocol deviations must adhere to the requirements of the governing IRB.

Subjects may continue to participate until the end of the study, unless the protocol deviations put the subject at risk or the subject's condition requires that they be discontinued from the study.

10 Study Materials and Management

Bausch + Lomb will provide all study materials at no charge to the Investigator. Sites will be provided with dispensing sets for both the Test and Control lenses. All other materials will be provided to the site prior to the start of the study.

Subjects will be given an adequate supply of study lenses to wear on a daily disposable basis for the duration of the study.

Subjects will be provided with lens cases in which to dry stack their used lenses. All used lenses and blister foils will be returned at 1 week (Visit 3), 1 Month (Visit 4), 3 Months (Visit 5), and Exit Visits and all unused lenses will be returned to the Sponsor at end of the study.

Subjects will be instructed to use their habitual rewetting drops as needed during the study. Use of other contact lenses or care products is not allowed.

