12.6 Protocol Deviations

The following protocol deviations will be classified as major deviations when reported in the case report forms.

- Ineligibility
- Non-dispensed subjects
- Misrandomization
- Dispensing or use of the incorrect lens type
- Dispensing of the incorrect lens power, defined as a discrepancy greater than 0.25D in sphere, cylinder, or spherical equivalent
- Non-compliance with the recommended wearing schedule, such as
 - wearing lenses less than 80% of the recommended time, or
 - wearing a lens for multiple days

- Use of medications that could potentially affect ocular physiology or lens performance
- Failure to comply with the procedures used to assess primary effectiveness endpoints, such as missing the assessment or failing to complete the procedure in accordance with the instructions provided by site personnel.

Additional major categories may be added prior to unmasking. Major deviations will be provided in a listing.

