12.7 Compliance

Subject compliance will be measured by reviewing diary entries and questioning the subject at each visit.

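### The Per Protocol exclusion for major deviations has no Visit 3 cut-off, so as worded a later deviation can remove a valid 1-week result from the primary analysis

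*Combined protocol and SAP*

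**What the plan says.** Section 12.2.2: "The PP Population will include all randomized subjects without major protocol deviations who complete the study through Visit 3 (Days 6 - 10". Its next sentence deals with one-eye deviations, for eye-level summaries only: "Major protocol deviations affecting only one eye will result in the exclusion of both eyes from eye level summaries".

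Section 12.6 classes listed deviations as major once they are reported in the case report forms, and gives no date limit. The list includes "wearing lenses less than 80% of the recommended time, or" as well as wearing one lens for several days, and use of medication that might affect the eye or the lens. It also includes "Failure to comply with the procedures used to assess primary effectiveness endpoints, such as missing the assessment". Further categories may be added until unmasking.

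Lens wear continues long after Visit 3. Section 7.2.1 states: "The 3-month follow-up visit must occur no earlier than Day 92". Section 12.7 states: "Subject compliance will be measured by reviewing diary entries and questioning the subject at each visit". Section 9.4 allows deviators to remain: "Subjects may continue to participate until the end of the study, unless the protocol deviations put the subject at risk".

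The primary endpoint is measured at the 1-week visit (11.4.1) and analysed in the PP Population without imputation (12.3.2). For classification, 12.3.2 and the synopsis make a subject with any eye above 0.04 a failure, and a subject with any eye missing unclassified. No order is given between the two rules.

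**The concern.** The primary outcome is complete by Day 10 at the latest, but membership of the set in which it is analysed stays open until the subject leaves the study. From the Day 8 target to the Day 92 target is 84 of the 91 days after dispensing (92%), so most opportunities for a wear or medication deviation come after the endpoint. Behaviour after the endpoint could then decide whose endpoint counts.

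That behaviour need not be independent of the result. Section 7.1 says of subjects: "Subjects will be dispensed product according to the treatment arm corresponding to their randomization and will be unmasked". A subject who sees poorly may wear the lenses less. If failures are removed more often than successes, both arms' success rates rise and a true deficit in the Test arm shrinks. If removal is unrelated to outcome there is no bias, only a smaller sample, and the 10% allowance in 12.1.2 is worded for dropouts.

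The classification overlap is a smaller gap of the same kind: the plan leaves to the analyst a choice that should be fixed before unmasking.

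**Working it through.** **Inputs from the plan** (12.1.1, 12.1.2, 12.3.2): success rate 0.925 in both arms, margin 10 points, one-sided alpha 0.025, 109 evaluable and 122 enrolled per arm, unpooled Wald limit without continuity correction. No deviation rates are given, so every rate below is an assumption.

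**The plan's own figure.** n = (1.960 + 0.842)² × 2 × 0.925 × 0.075 / 0.10² = 108.9, so 109 per arm. Power at 109 is 80.0%. 109/0.9 = 121.1, so 122 per arm and 244 in total. The plan's numbers reproduce.

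**Power if late deviation is unrelated to outcome.** Power = Φ(0.10/√(2 × 0.925 × 0.075/n) − 1.96). The exact figures enumerate two independent binomials at the rounded n.

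| Assumed loss from 122 per arm | n | Formula | Exact |
|---|---|---|---|
| 10% in total | 109.8 | 80.3% | 80.0% |
| 5% early, then 10% late | 104.3 | 78.3% | 79.0% |
| 10% early, then 10% late | 98.8 | 76.1% | 76.5% |

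**Type I error if late deviation is related to outcome.** Set the truth at the margin: Test 0.825, Control 0.925. Assume 5% early loss, leaving 122 × 0.95 = 115.9 per arm. Let a share s of 1-week successes and f of failures deviate later, with the same shares in both arms. The PP success rate is p(1−s) / [p(1−s) + (1−p)(1−f)]. For s = 10% and f = 15%, Test is 0.7425/0.89125 = 83.31% and Control is 0.8325/0.89625 = 92.89%, with n = 103 and 104.

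| s | f | Test v Control in PP | n | Exact type I error |
|---|---|---|---|---|
| 10% | 10% | 82.50 v 92.50 | 104/104 | 3.0% |
| 2% | 5% | 82.94 v 92.71 | 113/113 | 3.3% |
| 10% | 15% | 83.31 v 92.89 | 103/104 | 3.7% |
| 10% | 20% | 84.14 v 93.28 | 102/103 | 4.5% |
| 10% | 5% | 81.71 v 92.12 | 105/105 | 2.3% |

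The first row has no selection. Its 3.0% comes from the Wald test at this sample size (it is also 3.0% at 109 per arm), so only the departure from 3.0% belongs to this point.

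**What one subject can do near the margin** (illustrative counts). For 98/109 v 101/109 the difference is −2.75 points, the standard error 3.82 and the lower limit −10.23, which fails. Without one Test failure, 98/108 v 101/109 gives −9.26, which passes. Removing one Control failure instead (98/109 v 101/108) gives −10.93. The effect can go either way.

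**The classification overlap.** Success requires both eyes at 0.04 or better, so one observed eye above 0.04 settles the subject as a failure whatever the other eye would have read. The missing-value rule in 12.3.2 nevertheless also applies. The worst-eye rule in 12.3.1.1 is general, does not mention missing eyes and does not claim to override 12.3.2.

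**The case against.** The strongest reply is that 12.2.2 is a single sentence built around the endpoint visit and that any statistician would apply it up to that visit. Several items in 12.6 (ineligibility, misrandomization, a missed primary assessment) arise by Visit 3 in any case. The point depends on the wear and medication items, plus a wrong lens at a later replacement. Appendix B, which 11.1.7 cites for wearing restrictions, is not in the public text, so a period for the 80% rule may be set there. This makes the benign reading likely. It does not put it in the definition.

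The ITT analysis in 12.3.2 is also a real safeguard. It keeps late deviators, reports a 95% interval and, where data are missing, adds imputation with best-case, worst-case and tipping-point analyses. Selection could therefore show as a gap between PP and ITT. But it is a sensitivity analysis, and the primary conclusion would still rest on the affected set.

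Three stronger readings are tempting, and the documents do not support them.

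- A reader might infer serious error inflation. With 30% of failures and 10% of successes deviating late, the calculation gives 7.3%, but nothing in the plan suggests such rates. A subject who leaves after Visit 3 because of poor vision has completed Visit 3, so leaving is not in itself a PP exclusion.
- A reader might infer biased measurement from unmasked subjects. The Investigator is masked (9.1), so the risk shown here is selection.
- A reader might infer that the classification overlap threatens the primary analysis and that 12.6 must be rewritten to keep these subjects in PP. The case should be rare, since 11.1.3 provides spare lenses on site. A missed assessment is itself a major deviation, so the subject probably leaves PP under either rule. Keeping them has its own cost. At an assumed 5% random one-eye missingness, a true −10.0 becomes −10.2 (82.1% v 92.3%) if failures involve one eye only, or −10.4 (81.8% v 92.1%) if they involve both.

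**Conclusion.** The gap is real on the text: followed as written, 12.2.2 with 12.6 lets a deviation after Visit 3 remove a valid 1-week result from the only primary analysis. It is a gap in definition, not a sample-size error, and a Visit 3 limit was probably intended.

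Its size cannot be known from the documents. If total loss stays within 10%, power is unharmed. With 5% early and 10% late loss, power is about 78 to 79%. If late deviation is more common among failures, type I error rises by about 0.3 points (2% of successes v 5% of failures) to 1.5 points (10% v 20%) above a 3.0% baseline. If it is less common (10% v 5%), type I error falls to 2.3%. These figures assume equal deviation rates in both arms and a true difference at the margin.

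The classification overlap is a minor second point. It matters mainly in the ITT analysis, where it decides whether a subject is an observed failure or a value to be imputed and varied in the tipping-point analysis.

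**What to change.** In 12.2.2, change the condition to: *without major protocol deviations occurring on or before the Visit 3 VA assessment*. For PP membership, apply the 80% wear rule over the period from dispensing to that assessment.

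Before unmasking, add one sentence to 12.3.2 and the synopsis saying which classification rule prevails. The natural order is that any observed acuity above 0.04 makes the subject a failure, and missing is kept for subjects with at least one eye missing and no observed eye above 0.04. Stating either order removes the ambiguity. Section 12.6 can stay as it is.

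The cost is a wording amendment under 14.8. No new data are needed, because 9.4 already requires the date of every deviation, and the 109, 122 and 244 figures do not change. The one downside is that subjects who deviate only after Visit 3 stay in PP. That is small, because their 1-week result was obtained before the deviation.

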12.2.3 Safety Population

The Safety Population will include all dispensed subjects (all subjects fitted with contact lenses). In the Safety Population, subjects will be included in summaries under the lens type actually dispensed and used. If multiple lens types are dispensed and used including the test lens, then the subject will be included in summaries under the test lens treatment group.

